4.4. MEASURES TO MINIMIZE BIAS

4.4.1. Randomization

At screening, subjects will be assigned a subject identification number using a centralized electronic system (interactive web response system [IWRS]). When subjects are confirmed to be eligible for the clinical study, the subject will be randomized in a 2:1 ratio to GLPG1205 or placebo. Allocation of each subject to a given treatment will be done via IWRS and will be stratified for background standard of care (subjects receiving nintedanib, pirfenidone, or neither nintedanib nor pirfenidone).

4.4.2. Blinding and Unblinding

This is a randomized, double-blind study. The subject, investigator, clinical study coordinator and the entire clinical study team, will remain blinded to treatment assignment.

Blinded and packaged medication will be provided to the clinical center. All IMP formulations will be identical in appearance, shape, smell and taste, and packaged in the proper proportion to assure desired dosages and maintenance of the blinding.

The blind can be broken only if the investigator deems it necessary for the safety of a subject. The investigator is encouraged to discuss considerations to break the blind with the CRO medical monitor, whenever possible and where the situation allows. However, the responsibility to break the treatment code in emergency situations resides solely with the investigator. The investigator is not required to discuss unblinding beforehand if he or she feels rapid emergency unblinding is necessary but is required to inform the sponsor in a timely fashion after unblinding has occurred, without disclosing the treatment allocation to the team.

The blind can be broken by the investigator via IWRS.

All subjects who are unblinded while on the clinical study will be withdrawn at the moment of unblinding, with the reason for unblinding given as the reason for withdrawal from the clinical study. If an AE leads to unblinding, the AE will be given as the reason for unblinding, and the AE will be followed up as described in Section 9.3.1. All subjects who are unblinded should, where possible, complete the EOT visit and the follow-up visit, 4 weeks after EOT.

If necessary code-break information (via IWRS vendor) will be provided to the bioanalytical laboratory responsible for plasma drug determination sample analysis, and the sponsor pharmacovigilance lead for SAE reporting purposes.

An unblinded review of data will be performed on a regular basis by an IDMC. See Section 8 for further details.

An interim analysis may be performed in order to allow sponsor planning of following clinical studies, while maintaining the blind at an individual subject level. All efforts will be made to restrict the access to results so that personnel involved with the study conduct remains blinded to the extent possible. See Section 7.3.2 for further details.

5. INVESTIGATIONS MEDICINAL PRODUCTS

5.1. IDENTITY OF THE INVESTIGATIONS MEDICINAL PRODUCTS

The chemical name of GLPG1205 is 9-cyclopropylethynyl-2-((S)-1-[1,4]dioxan-2-Imethoxy)-6,7-dihydro-pyrimido[6,1-a]isoquinolin-4-one.

GLPG1205 will be provided as an oral hard gelatin capsule containing 50 mg of G321605 (active ingredient) or a matching placebo. Both active and placebo capsule will be identical in appearance, shape, smell and taste.

5.2. DOSAGE AND ADMINISTRATION

The following doses will be tested:

- GLPG1205 100 mg q.d. (as 2 capsules of 50 mg)
- Matching placebo q.d. (as 2 capsules)

The IMP is to be taken q.d. at approximately the same time every morning with or without food. Subjects will be instructed to swallow the capsules of GLPG1205 or placebo as a whole with a glass of water and to not chew the drug prior to swallowing. At the baseline visit, IMP will be administered on site after predose assessments have been completed. On all other visit days subjects also need to take their IMP on site. If subjects are taking pirfenidone or nintedanib then these must also be taken on site at Visit 2, Visit 4 and Visit 8 in order to perform appropriate PK sampling (see Section 6.6).

If a subject misses a dose (e.g. because he/she forgot to take the medication), he/she should take the missed dose within 5 hours after the planned intake time. If IMP is not taken within 5 hours after the planned time, the missed dose should be skipped. For each dose taken, the time, date and number of capsules taken should be recorded in the subject's diary card. During each visit, the investigator will record a summary of IMP intake data in the CRF.

In case of an AE at least possibly related to GLPG1205 as per the investigator's judgement requiring dose reduction, or in the case of intolerance to or toxicity of the IMP, subjects may have their dose of IMP reduced from 2 capsules q.d. (100 mg) to 1 capsule q.d. (50 mg) for the remainder of the study. Should the intolerance or toxicity continue, IMP may be discontinued, and the subject may be withdrawn from the study.

In the event of temporary interruption of IMP due to e.g. an AE, IMP can be re-introduced at the investigator's discretion, depending on the reason for interruption. The investigator should inform the medical monitor immediately of interruption or events leading to interruption in order to help with subject retention.

5.3. PACKAGING, LABELING AND DISTRIBUTION

An IMP kit will consist of 3 Alu/Alu blisters, each containing 12 capsules, packaged in an outer box and labeled with a clinical study-specific label. Each IMP kit contains medication to cover 2 weeks of treatment, including spares. All manufacturing, packaging, and labeling operations will be performed according to Good Manufacturing Practice for Medicinal Products and the relevant regulatory requirements.

The distribution will only occur after the required local documentation is obtained including clinical study approval by Competent Authorities and the Independent Ethics Committees (IECs)/Institutional Review Boards (IRBs), documentation on which the assessment of the investigator's qualifications was based (e.g. curriculum vitae) and the signed and dated study agreement and financial agreement.

Addendum for IMP Distribution:

Direct-to-patient (DTP) shipment of IMP due to Coronavirus disease 19 (COVID-19) pandemic

In case a subject is not able to visit the site for IMP resupply, DTP shipment of IMP can be implemented. DTP IMP shipment will follow the ICH GCP principles and be in compliance with national legislation. DTP IMP shipment will occur from an investigational site to the subject by a logistics provider in a traceable and preferably temperature-controlled manner and will be documented adequately. The patient will be asked to return any unused IMP and empty IMP packages by a logistics provider or during the next on-site visit.

5.4. STORAGE

Sites are to store the IMP (GLPG1205 and matching placebo) supplies in a secure area below +30°C (may not be frozen) until dispensed. Sites will be required to monitor the storage temperature by using at least a min-max temperature-recording device and to keep a minimum to maximum temperature log that is to be completed each working day in order to establish a record of compliance with these storage conditions. The investigator will instruct subjects on how the IMP should be stored at home after it is dispensed.

5.5. TREATMENT COMPLIANCE AND DRUG ACCOUNTABILITY

The pharmacist or designated clinical study personnel will maintain a log of the total amount of IMP received at site, amount dispensed to the subject, and the amount of IMP returned by the subject to the site. Drug supplies for each subject will be inventoried and accounted for

throughout the clinical study. At the end of the treatment period these records will be checked against the inventory by the study monitor. All clinical supplies will be stored in locked facilities.

Subjects will be given a diary card at every visit in the treatment period starting at Visit 2 (Day 1) to record the following:

- From Day 1 through Week 26, subjects will be asked to record the date, time and number of capsules taken
- From Day 1 through Week 26, subjects will be asked to record changes in concomitant medication regimen, including new medicines not captured in medication history, use of bronchodilators, use of pirfenidone or nintedanib, and any other concomitant medication used as well as any emerging AE.

Subjects will be instructed to bring their diary card and to return any unused IMP and empty IMP packages at each visit during the treatment period and/or EOT visit. A summary of the diary card data will be entered in the CRF by the designated site personnel. Missed doses should be discussed to try to ascertain the reason(s). Every effort should be made to ensure proper subject dosing.

Subjects with a poor compliance (<80% or >120%) will be retrained by the study site. If study drug compliance remains <80% or >120% between study visits, the subject will be evaluated for potential discontinuation. Any discontinuation should be done in consultation with the medical monitor.

Upon sponsor approval all unused IMP and empty IMP packages should be returned to the drug supplier/drug depot or will be destroyed at the site. In case of destruction by the site or the supplier/drug depot, an acceptable destruction process should be in place and a destruction certificate should be provided to the sponsor.

6. CLINICAL STUDY ASSESSMENTS

Every effort should be made to ensure that CSP-required tests and procedures are completed as described (see Section 6.10). To avoid inter-observer variability, every effort should be made to ensure that all safety and efficacy evaluations are completed by the same individual who made the initial baseline determinations.

6.1. TIMING OF ASSESSMENTS

The study assessments will be undertaken at time points as specified in the schedule of activities in Section 6.10. Screening assessments need to be performed within 28 days before Day 1 and may be split into multiple days or visits. A window of ± 2 days is allowed for Visit 3 and 4, a window of ± 4 days is allowed for Visit 5, 6, 7, 8 and 10; and a window of ± 6 days is allowed for Visit 9. All visits should preferably be performed in the morning.

If an on-site Visit 9 cannot be performed at the scheduled timepoint due to factors related to the COVID-19 pandemic, the visit window and the study medication intake period can be either extended up to +56 days or shortened up to -28 days, to allow flexibility in scheduling the visit. For more details and other visits see Section 6.1.1.

Retesting of individual screening assessment(s) that did not meet eligibility criteria is not permitted, with the following exceptions AND only in case it is still possible to randomize the subject within the per protocol-defined screening period of 28 days:

- Laboratory values for liver function tests, creatinine clearance, and hemoglobin can be retested once
- Lost or invalid blood or urine samples

Rescreening: in case of screening failure, subjects are allowed to be rescreened once, with an interval of at least 6 weeks. Subjects confirmed not to have a diagnosis of IPF by central reading may not be rescreened. If rescreened, the subject must be reconsented. The subject will be assigned a new subject number which will be linked to the first screening number.

The ICF needs to be signed before any study procedure, including screening procedure, is carried out.

During all visits the following should be taken into account with respect to timing of assessments (if applicable):

- SGRQ is recommended to be performed prior to any other visit-related procedures
- 12-lead ECG and vital signs are to be performed before spirometry
- Spirometry*, physical examination, 12-lead ECG and vital signs are to be performed before blood/urine sampling
- Spirometry* is to be performed preferably at approximately the same time every visit

Screening assessments need to be performed with the following considerations:

- Spirometry* can be repeated once at another screening visit (within the same planned screening period) if acceptability and repeatability criteria as specified by ATS/ERS/JRS/ALAT are not met as confirmed by central spirometry reader
- Safety blood/urine samples for clinical laboratory evaluations and physical examination, vital signs, 12-Lead ECG need to be available at the latest on Day -1
- Repeat spirometry can only proceed if IPF diagnosis per HRCT/LB is confirmed (according to the criteria in [Appendix 1](#))
- For sites that do not have a DLCO machine and need to refer to another site, it is recommended to perform the DLCO only once IPF diagnosis per HRCT/LB is confirmed (according to the criteria in [Appendix 1](#))
- If there is no historical HRCT available, a new HRCT needs to be planned and performed. Only if for logistic reasons it is not possible to perform a new HRCT within the planned screening period and after approval of the medical monitor it is allowed to extend the screening period with maximum 2 weeks

During the baseline visit (Visit 2) the following should be taken into account with respect to the timing of assessments:

- At baseline (Visit 2) all assessments are to be performed prior to dosing
- Spirometry* can be repeated once if confirmation acceptability and repeatability criteria as specified by ATS/ERS/JRS/ALAT are not met. This repeat spirometry must be performed before randomization

– [REDACTED]

- * Spirometry assessments should be performed prebronchodilator. Prebronchodilator spirometry is defined as spirometry testing performed for a subject who has:
- withheld their short-acting β -agonist (e.g. albuterol) or anticholinergic (e.g. ipratropium bromide) for >6 hours prior to the spirometry assessment AND
 - withheld their long-acting bronchodilator (e.g. salmeterol, formoterol) for ≥ 12 hours and other longer-acting agents (e.g. indacaterol, tiotropium) for ≥ 24 hours prior to the spirometry assessment

In case the subject is on bronchodilators, he/she can use the bronchodilator after spirometry assessments

Safety assessments should be repeated at other time points and additional assessments made if clinically indicated.

6.1.1. Description of Visits

Visit 1 (screening visit)

The following procedures and assessments (to be performed within 28 days before Day 1 and may be split into multiple days or visits) will be performed during screening:

1. Signing ICF
2. Provide subject participation card
3. Assign a subject identification number
4. Initial subject and disease characteristics (send chest HRCT [historical or plan new] and LB [if available] for central review, demographics, medical history/concurrent illnesses, alcohol consumption and smoking habits; check inclusion/exclusion criteria)
5. Physical examination (including weight and height)
6. AE assessment and concomitant medication (including verification of stable dose pirfenidone or nintedanib, if applicable)
7. 12-lead ECG
8. Vital signs (supine systolic blood pressure [SBP], diastolic blood pressure [DBP], heart rate, oral or tympanic body temperature, and respiratory rate)
9. Spirometry (and submit data to central reader)
10. Safety blood sampling for clinical laboratory evaluations (hematology, coagulation, clinical chemistry, serology, and if applicable FSH test and pregnancy test)
11. Safety urine sampling for clinical laboratory evaluations (urinalysis)
12. DLCO
13. 6MWT
14. Repeat spirometry if acceptability and repeatability criteria as specified by ATS/ERS/JRS/ALAT are not met after confirmation by central spirometry reader (after IPF diagnosis per HRCT/LB is confirmed according to the criteria in [Appendix 1](#))
15. Schedule all visit days with the subject

The following procedures and assessments will be performed during the dosing period and follow-up:

Visit 2 (baseline visit):

Subjects who are taking nintedanib or pirfenidone, should bring these to the site for onsite dosing.

1. Check inclusion/exclusion criteria
2. SGRQ
3. Physical examination
4. AE assessment and concomitant medication
5. 12-lead ECG (triplicate)
6. Vital signs (supine SBP, DBP, heart rate, oral or tympanic body temperature, and respiratory rate)
7. Spirometry (and submit data to central reader)
8. Predose PK blood sample (for GLPG1205, and if applicable nintedanib or pirfenidone concentration analysis)
9. Safety blood sampling for clinical laboratory evaluations (hematology, coagulation and clinical chemistry)
10. Safety urine sampling for clinical laboratory evaluations (urinalysis)
11. [REDACTED]
12. [REDACTED]
13. 6MWT [REDACTED]
14. [REDACTED]
15. Repeat spirometry if acceptability and repeatability criteria as specified by ATS/ERS/JRS/ALAT are not met after confirmation by central spirometry reader
16. Randomization if all in- and exclusion criteria are met)
17. Dispense subject diary and provide instructions on IMP intake, timing and storage
18. Dispense IMP
19. Dosing IMP and if applicable nintedanib or pirfenidone on site

Visit 3, 5, 6, and Visit 7 (if applicable)

Subjects who are taking nintedanib or pirfenidone can do this at home or on site according to their normal routine.

1. SGRQ (Visit 6)
2. Physical examination (Visit 3 and 6)
3. AE assessment and concomitant medication
4. 12-lead ECG (Visit 3 and 6, single)
5. Vital signs (supine SBP, DBP, heart rate, oral or tympanic body temperature, and respiratory rate)
6. Spirometry (Visit 5, 6 and 7)
7. PK blood sample (Visit 6: predose sample for GLPG1205, and if applicable postdose sample for nintedanib or pirfenidone concentration analyses)
8. Safety blood sampling for clinical laboratory evaluations (hematology, coagulation and clinical chemistry)
9. [REDACTED]

10. [REDACTED]
11. Safety urine sampling for clinical laboratory evaluations (urinalysis)
12. Dosing IMP on site
13. Dispense subject diary and provide instructions on IMP intake, timing and storage
14. Collect subject diary
15. Dispense IMP
16. Collect returned IMP and review IMP compliance

Visit 4 and Visit 8 (if applicable)

Subjects who are taking nintedanib or pirfenidone, should bring these to the site for onsite dosing.

1. Physical examination
2. AE assessment and concomitant medication
3. 12-lead ECG (Visit 8, single)
4. Vital signs (supine SBP, DBP, heart rate, oral or tympanic body temperature, and respiratory rate)
5. Spirometry
6. Predose PK blood sample (for GLPG1205, and if applicable nintedanib or pirfenidone concentration analysis)
7. Safety blood sampling for clinical laboratory evaluations (hematology, coagulation and clinical chemistry)
8. [REDACTED]
9. [REDACTED]
10. Safety urine sampling for clinical laboratory evaluations (urinalysis)
11. Dosing IMP and if applicable nintedanib or pirfenidone on site
12. Postdose PK blood sample (± 2 hour postdose sample for GLPG1205, and if applicable nintedanib or pirfenidone concentration analyses)
13. Dispense subject diary and provide instructions on IMP intake, timing and storage
14. Collect subject diary
15. Dispense IMP
16. Collect returned IMP and review IMP compliance

Addendum for Visit 3 to Visit 8:

Alternative approach due to COVID-19 pandemic

If a study participant cannot conduct a study visit on site, the investigator will follow an alternative visit approach to ensure the safety of the subject and will conduct a remote visit (e.g., phone call, virtual visit) or home visit, to evaluate the safety of the patient, and to decide whether continuation in the study is justifiable.

The investigator should at least discuss the following items and collect the following information as much as possible:

- the subject's general condition
- information on any adverse events (changes of ongoing or new events)
- information on study medication intake
- information on standard of care medication intake
- information on concomitant medication intake
- completion of subject diary pages and Quality of Life Questionnaire by the study subject.

The investigator should consider local laboratory testing, physical examination, vital signs and ECG, whenever possible. These local data will not become part of the clinical database. These results should be stored as part of the source documentation at the clinical site to be available as necessary. In case any of the results are deemed clinically significant by the investigator, the corresponding AE needs to be reported in the eCRF.

Visit 9/EOT and Visit 10/EOS (if applicable)

Subjects who are taking nintedanib or pirfenidone can do this at home or on site according to their normal routine.

1. SGRQ (Visit 9/EOT)
2. Physical examination (including weight)
3. AE assessment and concomitant medication
4. 12-lead ECG (single)
5. Vital signs (supine SBP, DBP, heart rate, oral or tympanic body temperature, and respiratory rate)
6. Spirometry
7. PK blood sample (Visit 9: predose sample for GLPG1205, and if applicable postdose sample for nintedanib or pirfenidone concentration analyses; Visit 10/EOS: for GLPG1205, and if applicable also for nintedanib or pirfenidone concentration analyses)
8. Safety blood sampling for clinical laboratory evaluations (hematology, coagulation and clinical chemistry)
9. [REDACTED]
10. [REDACTED]
11. Safety urine sampling for clinical laboratory evaluations (urinalysis)
12. Dosing IMP on site (Visit 9)
13. [REDACTED]
14. 6MWT [REDACTED] (Visit 9/EOT)
15. [REDACTED]
16. Collect subject diary (Visit 9/EOT)
17. Collect returned IMP and review IMP compliance (Visit 9/EOT)
18. Repeat spirometry if acceptability and repeatability criteria as specified by ATS/ERS/JRS/ALAT are not met after confirmation by central spirometry reader

Addendum for Early treatment discontinuation Visit (EOT)**Alternative approach due to COVID-19 pandemic**

In case of an early treatment discontinuation, the following EOS visit, planned regularly 28 days after the last IMP intake, can occur either earlier by up to 7 days or later up to 28 days to enable the conduct of the EOS Visit on site (for more details see below in the Visit 10/EOS addendum). In addition:

- if the decision to discontinue the treatment was made during an on-site visit, and without any safety findings or ongoing AEs, the EOS Visit may be performed remotely.
- if the decision to discontinue the treatment was not made during an on-site visit, or in case of any safety observations or ongoing AEs, an EOS Visit on site is required to monitor the safety of the subject. In addition, remote or home unscheduled visits should be conducted at least every 14 days, until the on-site EOS Visit can be performed.

Addendum for Visit 9:**Alternative approach due to COVID-19 pandemic**

- If Visit 9 cannot be conducted on site according to the original schedule of activities (Section 6.10; see also Section 6.1, “[Timing of Assessments](#)”) due to the COVID-19 pandemic, the treatment period can be extended up to +56 days or shortened up to -28 days to enable the conduct of Visit 9 on site.
- If the study treatment is prolonged beyond the originally planned Visit 9 date, remote (e.g., telephone contact, virtual contact) or home unscheduled visits should be conducted at the originally planned visit date, and thereafter at least every 14 days, to closely monitor the patient’s safety until the on-site visit can be performed.
- If no on-site visit is possible within the 56 days of treatment prolongation, then a remote or home visit should be planned and conducted within the extended Visit 9 window. However, every effort should be made to perform the end of study (EOS) Visit 10 on site. If this is not feasible the medical monitor or sponsor should be contacted.

Addendum for Visit 10/EOS:**Alternative approach due to COVID-19 pandemic**

- If Visit 10 cannot be conducted on site according to the original schedule of activities (Section 6.10; see also Section 6.1, “[Timing of Assessments](#)”) due to COVID-19 pandemic, the visit window can be extended up to +28 days or shortened up to -7 days to enable the conduct of Visit 10 on site.
- If the Visit 10 window is extended, a remote or home unscheduled visit 28 days after last IMP intake should be conducted and thereafter at least every 14 days, until the on-site visit can be performed.
- If within the +28 days of Visit 10 window prolongation no on-site visit is possible, and Visit 9/EOT was performed on site without relevant findings and/or safety concerns,

then Visit 10 may be performed remotely or at home within the respective visit window.

- If, however, Visit 9/EOT was conducted remotely or at home, or if relevant findings and/or safety concerns were reported, then Visit 10 will have to be performed on site. If this is not feasible the investigator shall contact the medical monitor or sponsor.

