6.2. UNSCHEDULED VISITS

If the subject has taken a bronchodilator before spirometry, the visit should be rescheduled within the defined visit window to allow spirometry assessment without bronchodilator.

[REDACTED] This extra site visit needs to be performed within the defined visit window and the subject should take his/her medication until the day of the last assessment.

Safety assessments should be repeated at other time points and additional assessments made if clinically indicated. If needed additional visits (on site, remote, or home visit) to assess safety should be conducted.

Addendum for Remote Unscheduled Visits: Approach due to COVID-19 pandemic

In case of visit window extensions beyond the originally planned visit dates for Visit 9 or Visit 10, unscheduled remote or home visits are to be conducted as described in Section 6.1.1.

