6.4.2. Quality of Life

The SGRQ is a 50-item paper questionnaire split into 3 domains:

- symptoms (assessing the frequency and severity of respiratory symptoms),
- activity (assessing the effects of breathlessness on mobility and physical activity),
- impact (assessing the psychosocial impact of the disease).

Scores are weighted such that every domain score and the total score range from 0 to 100, with higher scores indicating a poorer health-related quality of life.

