3.3.3. Analysis Windows

All assessments, including data collected on unscheduled visits, will be allocated to analysis windows based on the relative day of the assessment (see Section 3.3.1) and according to the algorithm in Table 2. TLFs will present the analysis windows.

Table 2 Analysis Windows for All Endpoints:

Time point label	Target day	Interval lower bound	Interval upper bound
Baseline	1	-INF	1
Week 2	15	2	22
Week 4	29	23	43
Week 8	57	44	71
Week 12	85	72	99
Week 16	113	100	127
Week 20	141	128	162
Week 26	183	163	197
Week 30	211	198	+INF

INF=infinity

Addendum: alternative approach due to COVID-19 pandemic

The Urgent Safety Measures (USMs dated 02-April-2020) described in CSP Amendment 2 allow to enlarge the visit window at the end of the treatment period (Visit 9, Week 26; from -28 days up to +56 days) including extension of study medication intake, i.e. up to a maximum of 56 days beyond 26 weeks of treatment. Hence, for patients having to extend treatment due to COVID-19, this could potentially result in end-of-treatment assessments being allocated to the FU/W30 analysis window and thus having missing data for the primary analysis time point W26. To assess the impact of this ‘missing’ data on the efficacy results, sensitivity analyses will be included in which these specific assessments are assigned to W26.

Definition of Baseline

For all endpoints, except ECG parameters and spirometry, baseline is defined as the last non-missing value before the first study drug administration. If multiple values qualify as last value, the mean of these values will be used in the analysis.

For spirometry endpoints, the mean of the analysis values (detailed in Section 5.2.2 for spirometry) before the first dose of study medication (including screening, baseline and unscheduled values as applicable) will be used to define the baseline value to reduce variability.

For electrocardiogram (ECG), the baseline is defined as the mean of the last recorded triplicate before the first study drug administration. If no triplicate is available before the first dose of study medication intake, the mean of the last duplicate ECG will be used, otherwise, the last ECG value will be considered as baseline.

Selection of Visits

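### When COVID-19 postpones Visit 9, the remote contact on the planned date does not list the SGRQ, so a delay of more than 14 days removes it from the Week 26 analysis

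*Protocol*

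**What the plan says.** - **Postponed Visit 9 (Protocol 6.1.1, Addendum for Visit 9).** Treatment and Visit 9 may be extended by up to 56 days. If they are, contacts are required, remotely or at home: "home unscheduled visits should be conducted at the originally planned visit date, and thereafter at least every 14 days, to closely monitor the" (cut here; what is monitored is how safe the subject is). The stated purpose ends with "safety until the on-site visit can be performed". No list of items to collect is given. Protocol 6.2 adds nothing: "unscheduled remote or home visits are to be conducted as described in Section 6.1.1".
- **No on-site visit within the 56 days.** In that case "then a remote or home visit should be planned and conducted within the extended Visit 9 window". Its content is not listed either.
- **Where the SGRQ sits.** The Visit 9/EOT procedures in 6.1.1 open with "SGRQ (Visit 9/EOT"). The schedule in 6.10 has the SGRQ at baseline, Visit 6 (Week 12) and Visit 9, or at EOT after early discontinuation. Visit 10 has none.
- **Remote Visits 3 to 8.** The addendum for these visits includes, among the items to collect as far as possible, "completion of subject diary pages and Quality of Life Questionnaire by the study subject". Within that range the SGRQ falls due only at Visit 6.
- **The form.** "The SGRQ is a 50-item paper questionnaire split into 3 domains" (Protocol 6.4.2).
- **The analysis.** SAP 3.3.3: "All assessments, including data collected on unscheduled visits, will be allocated to analysis windows based on the relative day of the assessment". Within a window, the value nearest the target day is used. Missing results are not imputed (SAP 3.4.1.2). SGRQ scores are compared by a separate ANCOVA at each planned time point (SAP 5.2.3.3).

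**The concern.** Change in SGRQ up to 26 weeks and the proportion of responders are secondary endpoints. For a subject who completes treatment, only two post-baseline questionnaires are scheduled, at Weeks 12 and 26. The pandemic amendment provides for remote completion at the first of these. At the second, which carries the endpoint, it requires a contact on the right day but does not ask for the form. A site that follows the text can therefore hold the contact on the planned Week 26 date, leave the SGRQ until the on-site visit, and collect it too late for the Week 26 window.

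Spirometry and the walk test are done at the study center, so their delay cannot be avoided in this way. The SGRQ is on paper, and the same amendment already has subjects complete it remotely.

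**Working it through.** **Inputs.** The Week 26 target is Day 183 (26 × 7 + 1), with an analysis window of Days 163 to 197; the Week 30 window starts on Day 198 (SAP 3.3.3, Table 2). The ordinary Visit 9 window is ±6 days and the COVID-19 extension is up to +56 days (Protocol 6.1 and 6.1.1). Protocol 7.1 assumes 40 and 20 evaluable subjects, 10% dropout, an SD of 200 mL, and true differences of 50 and 80 mL in a 50:50 mix. The originally planned date is taken as Day 183.

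**The plan's own figure.** The documents give no precision figure for the SGRQ. The only sample-size illustration is for FVC, and it confirms the numbers per arm. With 36 and 18 subjects after dropout, SE = 200 × √(1/36 + 1/18) = 57.7 mL, and the mean difference is 0.5 × 50 + 0.5 × 80 = 65 mL.
- P(observed > 40 mL) = 1 − Φ((40 − 65)/57.7) = 66.7%; the plan states 67%.
- P(observed > 20 mL) = 1 − Φ((20 − 65)/57.7) = 78.2%; the plan states 78%.

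**Where a postponed SGRQ lands.** The ordinary visit window, Days 177 to 189, lies inside the Week 26 window. The latest postponed Visit 9 is Day 183 + 56 = Day 239.
- Delay of 1 to 14 days: Days 184 to 197, Week 26 window.
- Delay of 15 to 56 days: Days 198 to 239, Week 30 window. This is 42 of the 56 permitted days.

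**Where the required contacts land**, if held exactly every 14 days:

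| Contact | Day | SAP window |
|---|---|---|
| Planned date | 183 | Week 26 |
| +14 days | 197 | Week 26 |
| +28 days | 211 | Week 30 |
| +42 days | 225 | Week 30 |
| +56 days | 239 | Week 30 |

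A form completed at the first contact is on the target day, and one completed 14 days later still falls in the window. If an on-site SGRQ also falls in the window, the nearest-to-target rule selects between the two, so a second form creates no ambiguity.

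**Effect on precision.** The documents do not say how many subjects had, or might have, a Visit 9 more than 14 days late, so the share x is an assumption. With the same share lost in both arms and the SD unchanged, the standard error is multiplied by √[(1/(36(1 − x)) + 1/(18(1 − x))) / (1/36 + 1/18)] = 1/√(1 − x).

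| Share lost, x (assumed) | Multiplier | Increase in SE |
|---|---|---|
| 5% | 1.026 | about 3% |
| 10% | 1.054 | about 5% |
| 20% | 1.118 | about 12% |
| 30% | 1.195 | about 20% |

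This counts precision only.

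**The case against.** Several points on the other side have force.

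- **The contacts are not restricted to safety.** A reader might infer that the Visit 9 addendum shuts the SGRQ out. It does not: it states a safety purpose but neither says that this is the sole purpose nor forbids the form. The Visit 3 to 8 addendum also gives safety as its purpose and still includes the questionnaire. What stands is that on-time collection is not required, so sites may differ.
- **A remote Visit 9 does not necessarily lose the SGRQ.** A reader might infer this because the content of the substitute visit is not listed. But the SGRQ is the first item of the Visit 9/EOT procedures, and nothing removes it when the visit is remote. Confirming this would be enough. A substitute visit held after Day 197 would still fall outside the Week 26 window.
- **The SAP saw the timing problem.** The COVID-19 addendum in SAP 3.3.3 recognizes that late end-of-treatment assessments may fall in the Week 30 window, and promises sensitivity analyses of the efficacy results that move them to Week 26. This answers the point only in part. SAP 5.2.2.2.4 spells the analysis out for the primary endpoint alone, and for the SGRQ it would substitute a value up to 8 weeks late.
- **The late form is not lost data.** It is still collected and can be reported in its own window. Part 1 of the questionnaire mostly asks about the past 3 months, so a late symptoms score still partly covers the time before Day 183. The items about the present do not share this protection.
- **Responders are less exposed.** SAP 5.2.3.3 counts a subject whose change reaches the threshold at least once. On that wording a Week 12 value may establish response.
- **The stakes are limited.** This is a secondary endpoint, without multiplicity adjustment, in a non-confirmatory study. The urgent measures date from April 2020 and the first protocol version from March 2018, so only subjects not yet past Visit 9 could be affected.

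**Conclusion.** The point holds as a gap in the Visit 9 addendum. A contact is required on the planned date, the SGRQ is not among its stated content, and the form therefore follows the on-site visit. Where that visit is 15 to 56 days late, the plan as written leaves the subject out of the Week 26 SGRQ ANCOVA, with no imputation and no reassignment specified for this endpoint. Delays of up to 14 days cost the analysis nothing.

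The size cannot be fixed from the documents. A loss of 10 to 20% in both arms is an assumption; it would raise the standard error of the Week 26 SGRQ difference by about 5 to 12%. The documents do not support the stronger conclusions that the SGRQ is barred from these contacts, that every remote Visit 9 goes without it, or that the responder analysis fails for every subject with a late Visit 9. The change is worth making because the loss is avoidable at very little cost, not because the trial's main conclusion depends on it.

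**What to change.** In the Addendum for Visit 9 (Protocol 6.1.1):

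1. Add completion of the SGRQ by the subject at the remote or home contact on the originally planned Visit 9 date (about Day 183), using the wording of the Visit 3 to 8 addendum.
2. Keep the SGRQ at the later on-site Visit 9.
3. Confirm that the SGRQ already listed for Visit 9 is also completed when Visit 9 itself is remote or at home.

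The cost is a sentence or two of protocol text and a posted paper form at a contact that already takes place. The downside is home rather than clinic completion, which the amendment already accepts at Week 12, and one extra questionnaire for some subjects. The SAP needs no change: it already takes in unscheduled-visit data and selects the value nearest the target day. The change does not help spirometry or the walk test.
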